***Correcting Residual Errors With Spectral, Ultrasound, Traditional Speech Therapy
(C-RESULTS-RCT)***

Protocol NCT03737318

Updated 12/8/2025

MASTER PROTOCOL FOR C-RESULTS RCT

Goal of study: Compare response to two types of visual biofeedback (ultrasound and visual-acoustic) versus traditional motor-based treatment for residual speech errors.

Primary outcome measure: Acoustically measured accuracy of within-session trials from Phase I (Acquisition).

Secondary outcome measure: Perceptually rated accuracy after Phase II (Generalization).

Functional outcome measure: Socioemotional questionnaire before vs after treatment.

Hypothesis: Mixed-effects models investigating the primary outcome measure will show a significant advantage for biofeedback over traditional motor-based treatment as early as the first day of Phase 1, and no later than the final day.

Enrollment: Target 55 kids in each of 2 sites (MSU, Syracuse), total n = 110

0. Pre-screening

- Phone screening to ask about all major exclusionary categories
 - Use Phone Screening Script
 - Additionally, review Parent Questionnaire for any responses that do not meet exclusionary criteria specified in Phone Screening Script.

1. Evaluation Session 1:

- Goal: Determine eligibility for inclusion in study; collect baseline measures for use in predicting response to treatment.
- See "Checklist for C-RESULTS Evaluation - Day 1"
 - Consent and assent; parent history form, demographic and socio-emotional questionnaires
 - Must be between 9;0 and 15;11 at time of enrollment.
 - Must have been exposed to English no later than age 3.
 - English must have equal or dominant status. Balanced bilinguals are okay.
 - Must speak a rhotic dialect of English; presence of one or more non-rhotic speakers in the home is exclusionary.
 - ADHD is admissible; other neurobehavioral disorders (ASD, OCD, Tourette's) are exclusionary.
 - History of CAS / learning disability / dyslexia is admissible if participant meets cutoff scores on eval day 1. Other developmental disorders are exclusionary.
 - History of permanent hearing loss is exclusionary. Temporary hearing loss due to otitis media, including recurrent OM/tubes, is admissible.
 - Hearing screening in soundbooth at 20 dB HL (500 Hz, 1000 Hz, 2000 Hz, and 4000 Hz)—must identify 2/3 tones at 20 dB at each frequency for inclusion.

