 - Probes for /r/: Sentence, Word, Stimulability
 - Rake-wake discrimination task
 - Bite block task
 - Category goodness task
 - Phonetic awareness task

4. Treatment targets

- Target variants:
 - syllabic /ɛ/, vocalic front vowel context, vocalic back vowel context, consonantal front vowel context, consonantal back vowel context.
- All participants will practice all variants in all phases of treatment.

5. Phase 0: Dynamic assessment

- Dynamic Assessment will consist of a single 90-minute session of traditional motor-based (non-biofeedback) instruction. The goal is to evaluate participants’ stimulability in detail and classify them into stimulability categories for randomization.

MASTER PROTOCOL FOR C-RESULTS RCT

- Same protocol as Phase I: Acquisition (see below), including both pre-practice and structured practice, but with no biofeedback.
 - Instruction (~25 min): Discuss tongue shapes for /r/. Use “Script_Introducing tongue shapes for r_Dynamic_Assessment_CRESULTS,” plus Tiede et al poster, followed by 2-minute break.
 - Pre-practice (until performance criterion met or session-level timer reaches 44 minutes): Relatively unstructured practice guided by the Prepractice Tally Sheet, with model and KP on every trial, followed by a 2-minute break.
 - Structured syllable practice (44 min).
- Based on the treating clinicians’ perceptual ratings of participants’ performance in Phase 0, participants will be categorized as high responders (>5% accuracy during Dynamic Assessment) or low responders (0-5% accuracy).

6. Randomization

- Overview:
 - Randomization will be supervised by the study statistician at the central site (NYU).
 - Randomization will be stratified by site and severity.
 - Randomization will be proportioned in a 3:3:4 ratio (ultrasound biofeedback : visual-acoustic biofeedback : traditional motor-based treatment) at each site.
- Approach:
 - The study statistician will generate confidential participant treatment assignments in batches of 10, where each batch of 10 corresponds to a combination of site (Montclair State University versus Syracuse University) and response category (high versus low).
 - Random assignments will be generated to ensure the following distribution per batch: 3 individuals assigned to receive visual-acoustic biofeedback, 3 to receive ultrasound biofeedback, and 4 to receive MBT.

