- Finally, we will analyze survey data using a similar model, with impact score as the outcome variable and fixed effects of time, treatment group, and the time-treatment interaction, as well as site, performance response category based on Dynamic Assessment, and pre-treatment accuracy. We will again estimate the interaction between time and treatment group to evaluate whether the functional impact of treatment differs across biofeedback versus MBT conditions.

13. Fidelity Checking Plan

- Treatment sites perform fidelity checks on each other to avoid breaking blinding for data site.
- Fidelity checks should be conducted on an ongoing basis.
- Randomly select a subset of sessions from each session type:
 - For DA, complete fidelity checks on 20% of subjects per site.
 - For Acquisition, randomly select one of the three sessions per subject per site.
 - For Generalization, randomly select one from the first half and one from the second half of treatment per subject per site.
- Re-score a subset of trials to check agreement across sites.
 - Re-score tone trials only in acquisition sessions slated for fidelity checking.

Data analysis plan

All analyses will be conducted following the intent-to-treat principle, comparing participants based on the treatment assigned regardless of subsequent exposure. To maintain the full sample, missing data will be multiply imputed for participants who drop out of the study using the *mice* package [45] in the R statistical software language [46]. This approach will capitalize on information collected on these participants prior to their loss to follow-up.

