To assess impact on our primary outcome, the acoustic accuracy measure of F3-F2 distance, we will fit a multilevel model using Phase 1 (Acquisition) data. The primary effect of interest is a comparison between MBT and biofeedback treatments, with visual-acoustic and ultrasound biofeedback types pooled for this analysis. This initial model will also adjust for site, performance response category (high responder versus low responder based on a Dynamic Assessment), Acquisition day (1, 2, or 3), and pre-treatment accuracy (mean F3-F2 distance across /i/ sounds in the word probe elicited in the first pre-treatment evaluation). If a within-session time trend is supported by the data, we will extend the model to account for time trends across trials within each day of treatment. Random intercepts will be included to reflect the fact that observations are nested within speakers and words, and random slopes that improve overall model fit (for speaker, acquisition day; for word, performance response category and pre-treatment accuracy) will be retained following model comparison using likelihood ratio tests.

Likelihood ratio tests will also be used to test the hypothesis of an advantage for biofeedback over MBT. Tests will be performed in two different model specifications. In one, the overall effect across days will be tested by focusing on the coefficient on the treatment variable. The other specification will interact the treatment variable with time in order to test whether the effect varies across days, since the hypothesized advantage for biofeedback over MBT could emerge as early as the first day or as late as the third day of Phase 1 (Acquisition). Although a positive effect of biofeedback is hypothesized, two-sided hypothesis tests will be used to be conservative.

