Our second analysis will fit a linear mixed-effects model using word probe data collected in one immediate pre-treatment and one immediate post-treatment session. The outcome variable will reflect the proportion of naïve listeners who rated the /i/ sound in a given production as correct. The model will include an indicator for time point (pre- versus post-treatment) and for treatment group (biofeedback versus MBT), as well as the interaction between them. As was the case for our primary measure, the model will adjust for site, performance response category based on Dynamic Assessment, and pre-treatment accuracy. Random intercepts for speaker, item (the 50 target words making up the probe measure), and listener will be included. Random slopes of response category and pre-treatment accuracy on word will be examined and included only as warranted by model comparison. As above, likelihood ratio tests will be used to assess the significance of the overall treatment effect. Again, while a positive effect of biofeedback is hypothesized, we will use a two-sided hypothesis test to be conservative.

For this second model, we will additionally test for the presence of a significant time-by-condition interaction in which the magnitude of improvement associated with biofeedback significantly is allowed to vary with time. If we observe a difference in our primary measure (Acquisition) but not our secondary measure (Generalization), this will be interpreted as evidence that biofeedback is more efficient, but not more effective, than MBT.

The final analysis will evaluate changes in impact scores from the 11-item survey assessing the social, emotional, and academic consequences of RSE from pre- to post-treatment time points. A mixed model similar to that used in the previous analyses will be fit including time (pre- versus post-treatment), treatment group (biofeedback versus MBT), and the time-treatment interaction as the primary predictors. The model will also adjust for site, performance response category based on Dynamic Assessment, and pre-treatment accuracy. We will again estimate the interaction between time and treatment group to evaluate whether the functional impact of treatment differs across biofeedback versus MBT conditions.

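### The randomisation strata enter only as main effects, so they do not adjust the treatment-by-time and treatment-by-day tests; adding strata-by-time terms is a free improvement, but the secondary model also needs a by-speaker slope for time

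*Combined protocol and SAP*

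**What the plan says.** **Randomisation (Section 6).** "Randomization will be stratified by site and severity". The approach paragraphs make clear that severity here means the high or low response category from the Dynamic Assessment: "each batch of 10 corresponds to a combination of site" and response category. "Randomization will be proportioned in a 3:3:4 ratio", so biofeedback pooled against motor-based treatment (MBT) is 6:4.

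**Models (Section 12 and the Data analysis plan).** Each model lists site, response category and pre-treatment accuracy as adjustment terms.
- **Primary, F3-F2 distance.** One specification tests the overall treatment coefficient. "The other specification will interact the treatment variable with time in order to test whether the effect varies across days". A by-speaker slope for acquisition day is kept only if it improves fit.
- **Secondary, listener-rated word probe.** The tested terms are time, group and their interaction, and "the model will adjust for site, performance response category based on Dynamic Assessment, and pre-treatment accuracy". Random intercepts are for speaker, item (50 words) and listener. The only random slopes considered are by word.
- **Survey.** Section 12 lists "fixed effects of time, treatment group, and the time-treatment interaction, as well as site, performance response category based on Dynamic Assessment" and pre-treatment accuracy.

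No model lists a fixed interaction of site or response category with time or day. The optional by-word slope of response category is not such a term.

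**The concern.** Treatment-by-day and time-by-treatment are within-child contrasts: they compare how much children change. A main effect of site or response category shifts all of a child's scores equally and cancels from that change. Batching within strata balances the arms on whatever the strata predict about improvement, yet the model still counts between-stratum differences in improvement as noise. A reader would take the adjustment sentence to cover these tests, and it does not.

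The interaction tests carry conclusions. The survey interaction is the functional result. The secondary result matters because the Data analysis plan reads a difference in Acquisition without one in Generalization as greater efficiency without greater effectiveness. A wrong SE in either direction bears on that reading.

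**Working it through.** The documents give no SE, alpha, power, effect size or SD, so there is no planned figure to reproduce.

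**Inputs from the documents.** "Enrollment: Target 55 kids in each of 2 sites (MSU, Syracuse), total n = 110"; 6:4 allocation, hence 66 and 44 children; four site-by-category cells; batches of 10; two-sided tests ("two-sided hypothesis tests will be used to be conservative"); 50 words per probe; one measured trial per block of 10 in Acquisition, about 15 to 20 per session at 150 to 200 trials.

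**Assumptions.** Alpha 0.05; complete data; near-equal strata; effect 0.5 SD of child-level change. R2 is the share of variance in change explained by the strata, placed on response category and varied from 0 to 0.30.

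**Step 1: does the main effect adjust the contrast?** A mixed model with a random child intercept was fitted to one simulated pre/post data set.

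| Fixed effects | Time-by-treatment estimate | SE |
|---|---|---|
| No strata | 0.4231 | 0.1919 |
| Strata as main effects (plan) | 0.4231 | 0.1919 |
| Strata-by-time terms added | 0.4073 | 0.1806 |

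The main effects change neither the estimate nor the SE.

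**Step 2: size with one score per time point (survey-type model).** With SD of change 1, the planned SE is 1/√(110 × 0.6 × 0.4) = 1/√26.4 = 0.195, and 0.5/0.195 = 2.57. Stratified allocation makes the true SD about 0.195 × √(1 − R2). Hence:
- SE inflation = 1/√(1 − R2)
- type I error = 2Φ(−1.96/√(1 − R2))
- power as planned = Φ((2.57 − 1.96)/√(1 − R2))
- power with the terms = Φ(2.57/√(1 − R2) − 1.96)

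| R2 | SE inflation | Type I error, plan | Power, plan | Power, with terms |
|---|---|---|---|---|
| 0 | 1.00 | 5.0% | 73% | 73% |
| 0.10 | 1.05 | 3.9% | 74% | 77% |
| 0.20 | 1.12 | 2.8% | 75% | 82% |
| 0.30 | 1.20 | 1.9% | 77% | 87% |

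Simulation with batches of 10 agrees. At R2 of 0.10, 0.20 and 0.30, type I error was 4.2%, 3.2% and 2.3% as planned and about 5% with the terms; power went from 71%, 74% and 76% to 75%, 81% and 86%, a gain of 4 to 10 points.

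**Step 3: primary treatment-by-day.** Simulated with 18 measured trials on each of 3 days and between-child SD of change of 0.2 to 0.6 residual SDs.
- By-speaker day slope kept: model SE over true SD is 1.02 to 1.08 at R2 = 0.20, slightly too wide.
- Slope dropped although children do differ: ratio 0.50 to 0.88, type I error 8% to 32%, too narrow.

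**Step 4: secondary model as written.** With a speaker intercept only and 50 words per probe, the model variance of a child's change is about 2σ²/50, while the true variance is τ² + 2σ²/50 (σ residual SD, τ between-child SD of change). The SE ratio is therefore about √[(2σ²/50)/(τ² + 2σ²/50)]. With σ = 0.25 and τ = 0.05 this is √(0.0025/0.0050) = 0.71; with σ = 0.35 and τ = 0.05 it is √(0.0049/0.0074) = 0.81. Simulation over σ of 0.25 to 0.35, τ of 0.05 to 0.20 and R2 of 0 or 0.20 gave ratios of 0.26 to 0.84 and type I error of about 10% to 61%.

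Time-by-strata terms alone do not repair this. At σ = 0.3 and R2 = 0.20, type I error without and with them was 11.6% and 11.7% (τ = 0.05), 27.8% and 27.5% (τ = 0.10), and 52.5% and 52.9% (τ = 0.20). With a by-speaker slope for time and no strata terms, the ratio at R2 = 0.20 was 1.03 to 1.10, the modest widening of Step 2, which the strata terms then address.

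**The case against.** The strongest objection is about direction. A reader might infer that all three interaction tests are conservative, and that a null secondary result would owe something to unused strata. The documents do not support that. The secondary model analyses individual productions and lists no by-speaker slope for time, so once children differ in improvement its SE is too narrow, by far more than the strata could widen it. Step 2 describes one score per time point and must not be carried over to that model. Treatment-by-day is too wide only if the day slope survives model selection. This objection stands, and it limits the point.

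A second objection is that the size is assumed. Response category is a single cut at 5% accuracy in one session without biofeedback; it describes starting status and need not predict change. This also stands: the documents do not give R2, and at zero there is no gain. It does not argue against the terms, since the trial already randomises by these factors and the terms then cost almost nothing.

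Nor should the point be read as a flaw in the overall primary test. That treatment coefficient is a between-child comparison, and the strata main effects do adjust it.

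**Conclusion.** The point holds in limited form, as a free improvement. The strata main effects do not adjust the interaction tests. If the strata predict improvement, the survey test is conservative, with type I error of about 4% to 2% for R2 of 10% to 30% and about 4 to 10 points of power to be recovered. The treatment-by-day test is slightly conservative if the day slope is kept. These errors cost power; they do not create false positives. The sizes rest on the assumptions listed in the check, including one survey score per time point.

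The secondary model is the exception. As written, its interaction SE is too narrow whenever children differ in how much they improve, and strata terms help there only together with a by-speaker slope for time.

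**What to change.** In Section 12 and the Data analysis plan:
1. Add time-by-site and time-by-response-category terms to the survey and secondary models.
2. Add day-by-site and day-by-response-category terms to the primary treatment-by-day specification.
3. Add a by-speaker random slope for time to the secondary model. Item 1 is of no use there without it.
4. Keep treatment-by-time or treatment-by-day as the tested effect.

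The cost is a few lines of wording, two degrees of freedom in each two-time-point model, four in the day model, and one further random-effect term in the secondary model. No extra data are needed.

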that observations are nested within speakers and words, and random slopes that improve overall model fit (for speaker, acquisition day; for word, performance response category and pre-treatment accuracy) will be retained following model comparison using likelihood ratio tests. Likelihood ratio tests will also be used to assess the significance of fixed effects and interactions in the final model. Likelihood ratio tests will also be used to test the hypothesis of an advantage for biofeedback over MBT. Tests will be performed in two different model specifications. In one, the overall effect across days will be tested by focusing on the coefficient on the treatment variable. The other specification will interact the treatment variable with time in order to test whether the effect varies across days, since the hypothesized advantage for biofeedback over MBT could emerge as early as the first day or as late as the third day of Phase 1 (Acquisition). Although a positive effect of biofeedback is hypothesized, two-sided hypothesis tests will be used to be conservative.

- For our secondary outcome (Generalization), we will use a linear mixed-effects model to examine word probe data collected in one immediate pre-treatment and one immediate post-treatment session. The outcome variable, “ \hat{p} -correct,” will reflect the proportion of naïve listeners who rated the /j/ sound in a given production as correct. Independent variables will include time point (pre- versus post-treatment) and treatment group (biofeedback versus MBT), as well as the interaction between them. As for our primary measure, the model will adjust for site, performance response category based on Dynamic Assessment, and pre-treatment accuracy. Random intercepts for speaker, item, and listener will be included. Random slopes of response category and pre-treatment accuracy on word will be included only as warranted by model comparison. As above, likelihood ratio tests will be used to assess the significance of fixed effects and interactions in the final model. Again, while a positive effect of biofeedback is hypothesized, we will use a two-sided hypothesis test to be conservative. For this second model, we will additionally test for the presence of a significant time-by-condition interaction in which the magnitude of improvement associated with biofeedback significantly is allowed to vary with time.

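### The secondary (Generalization) model has no by-child random slope for time, so its time-by-treatment test can give too many false positives if children differ appreciably in how much they improve

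*Combined protocol and SAP*

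**What the plan says.** The secondary analysis is described twice, in section 12 (Analysis Plan) and again under the later heading Data analysis plan. Section 12 states: "Random intercepts for speaker, item, and listener will be included". The Data analysis plan adds what an item is: "Random intercepts for speaker, item (the 50 target words making up the probe measure), and listener will be included". The only candidate slopes are by word: "Random slopes of response category and pre-treatment accuracy on word will be examined and included only as warranted by model comparison".

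The primary model differs. Both descriptions list among its candidates "random slopes that improve overall model fit (for speaker, acquisition day; for word, performance response category and pre-treatment accuracy"), so a by-child slope over time is available there. The phrases in the secondary analysis that refer back to the primary one bring across only the adjustment covariates and the use of likelihood ratio tests, not this slope.

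The two descriptions also differ on what is tested. Section 12 says that "likelihood ratio tests will be used to assess the significance of fixed effects and interactions in the final model". The Data analysis plan says that "likelihood ratio tests will be used to assess the significance of the overall treatment effect" and then that "we will additionally test for the presence of a significant time-by-condition interaction". If the primary outcome differs between arms and the secondary does not, "this will be interpreted as evidence that biofeedback is more efficient, but not more effective, than MBT".

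**The concern.** Each child is randomised once but supplies about 100 productions to this model. The interaction asks whether average improvement differs between arms, and the relevant yardstick is how much improvement varies from child to child. With only a child intercept, that variation goes into the residual and is averaged down as if it were independent across words. Site, response category and pre-treatment accuracy do not absorb it, because none is crossed with time. By-word slopes do not absorb it either.

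The trial itself expects children to respond differently. It collects baseline measures to predict response, sorts children into high and low responders after Phase 0, and stratifies randomisation on that category.

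If the interaction decides the secondary outcome, a chance difference between arms in how well comparable children respond can be declared a Generalization effect. The stated reading of a primary difference without a secondary one would then be lost to a false positive.

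**Working it through.** The plan gives no figure to reproduce: no significance level, power, SD or variance component for this outcome.

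**Inputs from the documents.** Total 110 children (opening summary). Allocation 3:3:4 (section 6), so pooled biofeedback versus MBT is 6:4, or 66 versus 44. Two time points and 50 words per probe (Data analysis plan).

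**Assumptions.** Two-sided 5% test, complete data, the same 50 words before and after, and one proportion per production. Let τ be the SD of true change among children in the same arm, site and response category, σ the residual SD, and g the SD of a stable child-by-word effect, all on the 0–1 scale.

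**True variance of the interaction.** A stable child-by-word effect cancels from each child's change, leaving

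V_true = (τ² + 2σ²/50) × (1/66 + 1/44), where 1/66 + 1/44 = 0.03788.

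**Variance the intercept-only model reports.**

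V_model = (2s²/50) × 0.03788, with s² = σ² + 0.9855g² + 0.249τ².

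The coefficients are expected residual sums of squares over residual degrees of freedom, 11,000 − 110 − 49 − 2 = 10,839: for g, 2 × 109 × 49 / 10,839 = 0.9855; for τ, 25 × 108 / 10,839 = 0.249.

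**Where the direction changes.** V_true = V_model when τ²(1 − 0.04 × 0.249) = 0.04 × 0.9855g², that is τ = 0.1995g. The standard error is too small when the SD of change exceeds about one fifth of the child-by-word SD, and too large below that.

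**Example, τ = 0.10, σ = 0.3, g = 0.2.**
- True SE = √[(0.0100 + 0.0036) × 0.03788] = 0.0227.
- s² = 0.09 + 0.03942 + 0.00249 = 0.1319, so model SE = √(0.04 × 0.1319 × 0.03788) = 0.0141.
- Ratio 1.61; false-positive rate 2[1 − Φ(1.96/1.605)] = 22.2%.

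**False-positive rate by closed form, σ = 0.3.**

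| SD of change τ | g = 0 | g = 0.2 | g = 0.3 |
|---|---|---|---|
| 0.02 | 6.3% | 2.6% | 0.9% |
| 0.05 | 13.1% | 7.0% | 3.4% |
| 0.10 | 30.7% | 22.2% | 15.2% |
| 0.20 | 55.3% | 48.3% | 41.5% |

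Over σ of 0.2–0.4 and g of 0–0.3 the ranges are 0.2–8%, 3–22%, 12–45% and 35–67% at τ of 0.02, 0.05, 0.10 and 0.20. For scale, τ = 0.10 means that about 95% of comparable children improve within 20 percentage points of the average (1.96 × 0.10).

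**Simulation under no treatment difference.** 20,000 replicates in each of 72 settings agree with the closed form within 0.7 percentage points. The alternatives behave as follows:
- By-child slope always included: 4.6–5.3% at τ of 0.10 or more, never above 5.3%, but well below 5% in places when τ is small and g is above 0.
- Slope kept only if a likelihood ratio test supports it: at most 7.1%.
- Slope plus child-by-word intercept: 4.2–5.3% in all settings.
- Child-level change scores: 4.6–5.3%.

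**The case against.** The omission itself is hard to dispute; the case on the other side is about its consequences.

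- **Size and direction rest on assumptions.** This stands. The plan's definition of item suggests the same words at both times, so some child-by-word variance is likely and the g = 0 column is an extreme. With g = 0.3 and σ = 0.3 the test is conservative at τ of 0.05 or below. But at τ of 0.10 or above the rate exceeded 5% in every setting tried, and a test whose error rate can drift either way is not controlled.
- **The unit of analysis is unresolved.** This also stands. A listener intercept cannot be fitted to a proportion already pooled over listeners, so the rates describe one reading and do not carry over to a model of individual ratings. More ratings per production would still not supply the missing child-level term.
- **The interaction may not be the deciding test.** A group coefficient averaged over both times would not be inflated by this omission. However, section 12 subjects interactions to testing, and the interaction is the only term that compares improvement between arms.
- **Stratified randomisation limits imbalance in responders.** True for the measured category. The calculation already defines τ within arm, site and category, so it concerns only the variation that stratification leaves.
- **It is a secondary outcome.** Correct, and the interpretation rule applies only if the primary outcome differs. That bears on severity, not on whether to correct it.

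**Conclusion.** The concern holds. Both descriptions leave a by-child slope for time out of the secondary model, and that part is certain. How far the interaction test is distorted cannot be fixed from the documents. Under the stated assumptions, an SD of change of 0.10 gives a false-positive rate of 12–45% for a nominal 5% test, while an SD of 0.05 or less can leave the test anywhere from conservative to clearly inflated. The primary analysis is not affected. This should be fixed before the secondary outcome is analysed, because a prespecified conclusion depends on it.

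**What to change.** In section 12 and in the Data analysis plan, add a by-child random slope for time to the secondary model. Including it by default is preferable; offering it as a likelihood-ratio candidate, as the primary model does, is the minimum and leaves a rate of up to 7.1% in the simulations. Child-level change scores serve the same purpose. A child-level post-treatment mean adjusted for the pre-treatment mean is a valid alternative, though a different estimator. A child-by-word intercept may be added to remove the conservatism that remains when children differ little in change.

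State in both places that the time-by-treatment contrast is the test of the secondary outcome, and whether the model is fitted to proportions or to individual ratings.

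The cost is SAP wording and one model term, with no new data. Intervals widen when change varies appreciably: in a single fitted dataset with τ 0.10, σ 0.3 and g 0.2, the interaction SE went from 0.0140 to 0.0233 with the slope, and change scores also gave 0.0233. With τ 0.02 and the same σ and g, it stayed at 0.0138 with the slope, while change scores gave 0.0123.
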